2.5.4 Windows for time points

The following steps will decide how the scheduled and/or unscheduled visits will be used in the analyses on efficacy variables and the by-visit summaries for safety variables (clinical laboratory data in [Section 2.1.4.4](#) and vital signs in [Section 2.1.4.5](#)).

Step 1: A scheduled measurement will be used if it is available; otherwise, an unscheduled measurement (including the end of treatment/study visit for those prematurely discontinued) will be used if it happens to be on the same date as the date of the scheduled visit.

Step 2: After Step 1, if there is still no measurement for a given parameter at a scheduled visit, the analysis window below ([Table 4](#)) will be applied to re-allocate a postbaseline unscheduled measurement to a scheduled measurement.

Table 4 - Analyses window definition

Scheduled visit post baseline	Targeted study day	Analysis window in study days
Week 2 (V s t 4)	14	2 to 20
Week 4 (V s t 5)	28	21 to 41
Week 8 (V s t 6)	56	42 to 69
Week 12 (V s t 7)	84	70 to 104
Week 18 (V s t 9)	126	105 to 153

COVANCE INC. CONFIDENTIAL

Scheduled visit post baseline	Targeted study day	Analysis window in study days
Week 26 (V s t 10)	182	154 to 227
Week 39 (V s t 11)	273	228 to 318
Week 52 (V s t 12)	364	≥319

Study days are calculated from the day of first administration of double-blind MP (or the day of randomization if not exposed) is Day 1

After applying the above time windows, if multiple assessments are associated to the same time point, the closest from the targeted study day will be used. In case of equality, the last measurement will be used. Re-allocated scheduled visits (ie, visit numbers) should be sequential if ordered by the date of measurement.

After Step 2, if there is still no measurement for a given parameter at a scheduled visit, data are considered missing for efficacy analyses, where MI would be applied as appropriately as described in [Section 2.4.4](#).

Reference day

The reference day for the calculation of extent of exposure, time to onset, and relative days will be the day of the first administration of double-blind IMP or the day of randomization if not exposed to double-blind IMP, denoted as Day 1.

Baseline definition for efficacy/safety data

For the safety analyses, the baseline for a given parameter is defined as the last available measurement (or the average of all measurements for creatinine and eGFR), including unscheduled assessments, assessed prior to the first administration of double-blind IMP. For the efficacy analyses, the baseline for a given parameter is defined as the last available measurement (or the average of all measurements for creatinine and eGFR), including unscheduled assessments, assessed prior to the first administration of double-blind IMP or the last available value (or the average of all measurements for creatinine and eGFR) before randomization if not treated with double-blind IMP.

Summary statistics by visit for continuous efficacy endpoints

Summary statistics (number, mean, SD, SE, minimum, median, maximum) of continuous efficacy endpoints (observed data and change from baseline) will be provided at scheduled visits as per protocol. Summaries showing data by visit will be presented according to the visit number (or re-allocated visit number, see [Section 2.5.4](#)) and labeled with the targeted approximate day/week.

Last on-treatment value for laboratory variables and vital signs

The last on-treatment value is the final measurement assessed during the treatment epoch, regardless of the introduction of rescue therapy, including measurements at unscheduled visits. Please see details in [Section 2.1.4](#) and [Section 2.4.5](#).

Display of safety data by visit (laboratory variables and vital signs)

Descriptive statistics (number, mean, SD, minimum, median, maximum) of quantitative laboratory variables and vital signs (observed data and change from baseline) during the TEAE period will be provided at scheduled visits. In addition, these summaries will also include a row for the “last value on-treatment” to describe the last available on-treatment value (see above). Summaries showing data by visit will be presented according to the visit number (or re-allocated visit number, see [Section 2.5.4](#)) and labeled with the targeted approximate day/week.

As specified in the study protocol, laboratory data from scheduled visits are reported by central laboratories. The local results will not be used in the efficacy analyses or in the definition of baseline for both safety and efficacy analyses. In the safety analyses, local results will only be used in the PCSA summary if they are accompanied by a local laboratory normal range.

When a patient has more than one measurement from the central laboratory for the same laboratory parameter on the same date, the average of the measurements will be used. For the same laboratory parameter, if a patient has more than one measurement on different dates for the same scheduled visit, the value closest to the date of the visit will be used for the scheduled visit. When the values for the same scheduled visit are equidistant, the last value should be used for the scheduled visit. Similar rules will be applicable to a patient who has more than one set of measurements for the same vital sign parameter (ie, SBP, DBP, or HR) on the same date.

Time-to-event analysis

For time-to-event analysis/KM plot, time-to-event (eg, treatment discontinuation, rescue therapy, hypoglycemia, etc) is defined as the number of days from the date of the first administration of double-blind IMP (or the date of randomization if not exposed) to the start date of the first occurrence of the event during the 52-week double-blind treatment period.

Patients who did not experience any event during the 52-week double-blind Treatment Period are considered censored observations. For time-to-treatment discontinuation/rescue therapy, censoring date is the date of EOT. For time-to-severe or documented hypoglycemia, censoring date is date of EOT + 1 or date of EOS, whichever is the earliest. Date of EOS will be used if date of EOT is not available. Last contact date will be used if date of EOS is not available.

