Abbreviations: AE = adverse event; AESI = adverse event of special interest; BP = blood pressure; ECG = electrocardiogram; eGFR = estimated glomerular filtration rate; EOSI = events of special interest; EOT = end of treatment; EW = early withdrawal; FPG = fasting plasma glucose; FSH = follicle-stimulating hormone; HbA1c = hemoglobin A1c; IMP = investigational medicinal product; IRT = Interactive Response Technology; NIMP = non-investigational medicinal product; PRO = patient-reported outcome; PQAT = Patient Qualitative Assessment of Treatment; SAE = serious adverse event; SMBG = self-monitoring blood glucose; UTI = urinary tract infection; WOCBP = women of childbearing potential

- a All visits' dates will be scheduled based on the date of randomization within visit window allowed as per flowchart. If a patient discontinues treatment with investigational medicinal product (IMP) during the Treatment Period, the patient will have a visit as soon as possible to complete the assessments normally planned for the last dosing day with the IMP [End of Treatment/Early Withdrawal (EOT/EW) Visit], and a Follow-up Visit 2 weeks after the last dose of IMP. In addition, every effort will be made to have the patients return to the site at the time corresponding to their scheduled visits, particularly the Week 26 and Week 52 visits. If the patient does not agree to a site visit, they will be contacted by telephone to inquire about safety status.
- b All patients will have a phone call Follow-up Visit 2 weeks after the last dose of the IMP to collect safety information.

- c Height to be measured only at Screening.
  - d Vital sign measurements (sitting BP, heart rate, temperature, and respiratory rate): 3 separate seated BP and heart rate measurements should be taken with at least 1 minute between readings, following a 5-minute rest period and prior to phlebotomy (see Appendix C).
  - e Patients will measure their fasting glucose levels via SMBG and discuss results with site personnel at clinic or phone visits, or **unscheduled** phone contacts. The SMBG measurements obtained with glucose meters are displayed as plasma glucose concentration. From randomization through Week 18, glimepiride or glimepiride-matching placebo dose adjustments will be made based on algorithm provided in protocol.  

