#### **10.3.4 Handling of patients after permanent treatment discontinuation**

Every effort should be made to maintain patients in the study. Patients should be followed-up according to the study procedures specified in this protocol up to the scheduled date of study completion, or up to recovery or stabilization of any AE to be followed-up as specified in this protocol, whichever comes later.

If a patient decides to discontinue IMP early, a Premature EOT visit (see Section 10.1.2.4) should be scheduled prior to treatment discontinuation, if possible. If not possible, the Premature EOT visit should be scheduled as soon as possible after treatment discontinuation. For patients that discontinue treatment but remain in the study, remaining study visits should occur as scheduled where possible. The IRT should be notified of EOT.

After permanent treatment discontinuation, of the investigational products, any treatments (other than SGLT2 inhibitors) are permitted, as deemed necessary by the Investigator.

All confirmed cases of permanent treatment discontinuation should be recorded by the Investigator in the appropriate pages of the e-CRF.

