2.4.4.1 Analysis of primary efficacy endpoint(s)

For the primary efficacy endpoint, the following null and alternative hypotheses will be tested:

- $H_0: \mu_T - \mu_C \geq 0.3\%$.
- $H_1: \mu_T - \mu_C < 0.3\%$.

Where μ_T and μ_C are the mean changes from Baseline in HbA1c at Week 52 for sotagliflozin and glimepiride groups, respectively.

The null hypothesis will be tested at a 1-sided alpha level of 0.025 using a non-inferiority margin of 0.3% of HbA1c change by comparing the upper bound of the 2-sided 95% CI for the adjusted mean treatment difference between sotagliflozin and glimepiride with 0.3%.

Primary analysis

The primary efficacy endpoint of change in HbA1c from Baseline to Week 52 will be analyzed by an Analysis of Covariance (ANCOVA) model using HbA1c values measured at baseline and Week 52 (observed or imputed). The missing data at endpoint will be imputed by multiple imputation (MI) methods as detailed below. To be concise, the following texts related to imputation are generalized to accommodate primary as well as continuous secondary efficacy endpoints.

Missing endpoint data at Week 52 or Week 26 (or Week 12 for SBP) visit will be imputed using a model built separately in each treatment group and estimated from the patients in the same treatment group who prematurely discontinue the IMP before the Week 52 or Week 26 (or Week 12 for SBP) visit but have measurements for the endpoint (ie, retrieved dropouts). The imputation model will include the randomization strata and the corresponding baseline value. In cases of non-convergence during the imputations, the offending stratum will be identified and then will be dropped from the model. Considering that the number of retrieved dropout patients in each treatment group is expected to be small, a simple imputation model based on regression will be used with baseline measurement included as the predictor. This will serve as the primary model of imputation for missing data should sampling criteria be satisfied (see below).

An alternative (back-up) imputation method will be used if the number of patients who prematurely discontinue the IMP before the Week 52 or Week 26 (or Week 12 for SBP) visit but have measurements for the endpoint is less than five (< 5) in any treatment groups (ie, insufficient number of retrieved dropouts to support the imputation method described above). This criterion will be assessed for each primary or continuous secondary efficacy endpoint separately.

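### Retrieved-dropout imputation does not separate on-drug from off-drug patients: some donors may carry on-drug end-of-treatment readings, and patients still on drug are imputed as if they had stopped

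*SAP*

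**What the plan says.** SAP 2.4.4.1 sets the primary imputation rule: "Missing endpoint data at Week 52 or Week 26 (or Week 12 for SBP) visit will be imputed using a model built separately", one model per arm. The model is estimated from same-arm patients "who prematurely discontinue the IMP before the Week 52 or Week 26 (or Week 12 for SBP) visit but have measurements for the endpoint", whom the SAP calls retrieved dropouts. If any group has fewer than five of them, a placebo-based washout method is used instead. The same rule serves the continuous secondary endpoints (SAP 2.4.4.2 and 2.5.2).

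SAP 2.5.4 decides what counts as a measurement at a visit. Step 1 describes unscheduled measurements as "including the end of treatment/study visit for those prematurely discontinued" and uses one if it falls on the scheduled visit date. If the visit still has no value, Step 2 says an analysis window "will be applied to re-allocate a postbaseline unscheduled measurement to a scheduled measurement". Table 4 gives the windows: days 70 to 104 for Week 12, 154 to 227 for Week 26, and day 319 onward for Week 52.

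Protocol 10.3.4 says the premature end-of-treatment visit "should be scheduled prior to treatment discontinuation, if possible", and otherwise as soon as possible afterwards. Footnote a of the flow chart (Protocol 1.2) says the patient attends to "complete the assessments normally planned for the last dosing day with the IMP".

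**The concern.** The retrieved-dropout model is meant to describe patients who are off drug at the visit. Read together, the passages break that in two ways.

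- **Donors.** A patient who has the end-of-treatment visit at day 330, stops, and does not return gets a Week 52 value by windowing. That patient then meets the donor definition, although the value reflects treatment. Such donors make other imputed dropouts look more treated than they were.
- **Recipients.** A patient still taking drug who misses the visit is imputed from patients who stopped, because the rule does not split by treatment status. This makes an effective arm look worse. The SAP foresees such patients: its analysis of 52-week treatment completers (2.4.4.1) includes an imputation step.

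At stake are the primary non-inferiority test and every continuous endpoint in the fixed sequence, together with the five-per-arm count that decides which imputation method is used.

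**Working it through.** **Inputs from the documents.** SD 1.1%, 310 or 155 patients per arm, margin 0.3%, 30% dropout (Protocol 11.1). Windows from SAP Table 4. Phase 2 changes at 12 weeks of -0.93% (400 mg), -0.48% (200 mg) and -0.14% (placebo) (Protocol 4.3), giving differences from placebo of 0.79 and 0.34.

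**The plan's own figure.** The plan gives none for donors. Its completer power is reproduced to confirm the inputs: 310 × 0.7 = 217 per arm; 0.3 / (1.1 × √(2/217)) - 1.96 = 0.88, or 81.1% power against the stated 80%.

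**Donors from end-of-treatment readings.** The scheduled Week 52 visit covers days 361 to 367 (Protocol 10.1), so the exposed stopping days are 319 to 360. If stopping is uniform over time (assumption), the share is 42/363 = 11.6%. The same reasoning gives 25/181 = 13.8% for Week 26 and 11/83 = 13.3% for Week 12. Upper limits per arm at Week 52, if none of these patients returns:

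| Stopping | 310-patient arm | 155-patient arm |
|---|---|---|
| 10% | 3.6 | 1.8 |
| 20% | 7.2 | 3.6 |
| 30% | 10.8 | 5.4 |

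**Recipients still on drug.** If a fraction k of an arm is on drug with a missing value and the on/off difference is D, the arm mean is too high by k × D. With k = 1-5% and D = 0.34-0.79, that is 0.003 to 0.040 points.

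**Both together.** One 310-patient arm was simulated with donor-mean imputation and no baseline regression. Apart from the SD, all settings are assumptions: on-drug change -0.8, off-drug change -0.1, uniform stopping, 10-30% stopping, 30-70% of stoppers returning at Week 52, and 0-5% of on-drug patients missing Week 52. All end-of-treatment readings in the window were treated as on drug.

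- End-of-treatment readings formed about 5-21% of donors.
- Lowest bias (30% stop, 30% return, 0% on-drug missing): -0.635 - (-0.590) = -0.045.
- Highest bias (10% stop, 70% return, 5% on-drug missing): -0.705 - (-0.730) = +0.025.
- With end-of-treatment readings set aside entirely and on-drug patients imputed from on-drug patients, the bias was within 0.005 of zero.

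**Splitting the worst case.** Of the -0.045, the windowed patients' own values contribute 7.57 × (-0.7) / 310 = -0.017. Contaminated donors contribute the rest: (93 × 0.7 - 7.57) = 57.5 recipients × 0.214 × (-0.7) / 310 = -0.028.

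**The case against.** The strongest reply is that the effect is small. The largest simulated bias is 0.045/0.3 = 15% of the margin in one arm, before any cancellation between two active arms. Against placebo, the planned differences are 0.5-0.6 points with at least 95% power. This stands, and no conclusion is shown to change.

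Second, not every end-of-treatment reading is on drug. Protocol 10.3.4 allows the visit after stopping, and 10.3.3 mentions only that timing. This also stands, more for blood pressure and weight than for HbA1c, which Protocol 9.5 says documents control over the past 2 to 12 weeks.

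Third, the SAP plans a washout analysis and tipping-point analyses. Washout does remove the active-arm donors, and the tipping point does stress the imputed sotagliflozin HbA1c values. But washout keeps windowed end-of-treatment values as observed and still imputes on-drug patients as untreated. The tipping-point penalty applies only to patients without Week 52 HbA1c, and no tipping-point analysis is planned for weight or blood pressure. Neither separates on-drug from off-drug readings.

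Fourth, the end-of-treatment wording sits in Step 1, which acts only on same-date readings. Step 2 does the re-allocation, and its reach to these visits is inferred from Step 1's description of unscheduled measurements. That is the natural reading, but the text could be clearer.

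A reader might infer that on-drug readings alone would satisfy the five-donor criterion. At 20% stopping and 20% return this fails. The criterion must hold in every arm, and a 155-patient arm expects 155 × 0.2 × 0.8 × 0.116 = 2.9 such readings. True returners already number 155 × 0.2 × 0.2 = 6.2 there, and 12.4 in a 310-patient arm. A change of method would need fewer returners than that.

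**Conclusion.** The gap is real and follows from the SAP's wording: donor status does not depend on when the reading was taken, and recipient status does not depend on whether the patient is still on drug. Under the assumptions above, the net bias is roughly -0.045 to +0.025 HbA1c points per active arm.

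A reader might infer a consistent advantage for sotagliflozin. The documents do not support that, because contaminated donors lower the arm mean while imputing on-drug patients as stopped raises it. Between sotagliflozin and glimepiride the bias partly cancels. Against placebo it does not cancel in the same way, because the placebo arm has no drug effect to mix.

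The size depends on stopping being uniform, on how many stoppers return, and on how many end-of-treatment readings are truly on drug, none of which the documents give. This is worth correcting because the rule is imprecise and cheap to repair, not because it threatens the trial's conclusion.

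**What to change.** 1. In SAP 2.4.4.1, define retrieved-dropout donors as patients whose endpoint reading was taken after the last dose, excluding readings from the end-of-treatment visit. Use the same definition for the five-per-arm count. Keep a windowed end-of-treatment reading as that patient's own observed value.
2. Impute patients still on drug at the visit from same-arm on-drug patients. Use the retrieved-dropout model only for patients who stopped.
3. State in SAP 2.5.4 that Step 2 applies to end-of-treatment readings, and report donors per arm by visit type and time since last dose.

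Two stricter rules are not recommended. Barring re-allocation would discard observed values close to the target day, against SAP 2.1.3 and 2.4.4, which use all collected efficacy measurements. Requiring more than 10 days since the last dose borrows a half-life-based safety window (Protocol 9.2) and would not make HbA1c off-drug.

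Keeping the patient's own windowed value leaves part of the bias: in the simulated settings, from 1.05 × 0.7 / 310 = 0.002 to 0.017 points. That overstates it, since a patient who stopped between days 319 and 360 has been off drug for only 4 to 45 days at day 364.

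The cost is SAP wording and a comparison of assessment date with last-dose date, both in the data. Donors become slightly fewer, so the washout back-up may be triggered more often. This SAP version (03-Apr-2020) postdates database lock (12 September 2019), so any change should be dated and shown beside the analysis as written.

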2.5.5 Unscheduled visits

Unscheduled visit measurements of laboratory data, vital signs, and ECG will be used for computation of baseline, the last on-treatment value, PCSAs and the shift summaries for safety or efficacy. They will be included in the by-visit summaries if they are re-allocated to scheduled visits (see [Section 2.5.4](#)).

2.5.6 Pooling of centers for statistical analyses

Center will not be included in the statistical models for efficacy analyses. However, all centers within a country will be pooled, and country will be included as a fixed effect in a parametric statistical model (eg, ANCOVA model) for the primary and secondary efficacy endpoints. Countries with fewer than five randomized patients will be grouped with the country with the lowest number of patients that is five or more.

2.5.7 Statistical technical issues

None.

3 INTERIM ANALYSIS

There are no formal interim analyses for efficacy planned for this study. The study will not be terminated early for excellent efficacy.

An independent Data Monitoring Committee (DMC) will be used to monitor and assess the safety of patients from this trial through periodic review of the accumulated safety data provided by an independent statistical group. Related details are provided in separate documents (DMC Charter and DMC SAP).

4 DATABASE LOCK

The database lock was on the 12Sep2019.

5 SOFTWARE DOCUMENTATION

All summaries and statistical analyses will be generated using SAS® Version 9.2 or higher.

Appendix A Mapping of inclusion and exclusion criteria under the original protocol and amendment

Order	Original Protocol	Amendment 1	CSR Display
1	I01		I01
2	I02		I02
3	E01		E01
4	E02		E02
5	E03		E03
6	E04		E04
7	E05		E05
8	E06		E06
9	E07		E07
10	E08		E08
11	E09		E09
12	E10		E10
13	E11		E11
14	E12		E12
15	E13		E13
16	E14		E14
17	E15		E15
18	E16		E16
19	E17		E17
20	E18		E18
21	E19		E19
22	E20		E20
23	E21		E21
24	E22		E22
25	E23		E23
26	E24		E24
27	E25		E25
28	E26		E26
29	E27		E27
30	E28		E28
31	E29		E29
32	E30		E30
33	E31		E31
34	E32		E32
35	E33		E33
36	E34		E34
37	E35		E35
38	E36		E36
39	E37		E37
40	E38		E38

Statistical Analysis Plan

Version:3

Lexicon Pharmaceuticals, inc. Protocol No. EFC14838

Date of Issue: 03-Apr-2020

Covance Study ID: 000000155206

Order	Original Protocol	Amendment 1	CSR Display
41		E39	E39

Appendix B Potentially clinically significant abnormalities criteria

CRITERIA for POTENTIALLY CLINICALLY SIGNIFICANT ABNORMALITIES
for Phase 2/3 studies (oncology excepted)
(From BTD-009536 May 21, 2014)

Parameter	PCSA	Comments
Clinical Chemistry		
ALT	By d str but on ana ys s : >3 ULN >5 ULN >10 ULN >20 ULN	Enzymes act v t es must be expressed n ULN, not n IU/L. Concept paper on DILI - FDA draft Gu dance Oct 2007. Interna DILI WG Oct 2008. Categor es are cumu at ve. F rst row s mandatory. Rows fo ow ng one ment on ng zero can be de eted.
AST	By d str but on ana ys s : >3 ULN >5 ULN >10 ULN >20 ULN	Enzymes act v t es must be expressed n ULN, not n IU/L. Concept paper on DILI - FDA draft Gu dance Oct 2007. Interna DILI WG Oct 2008. Categor es are cumu at ve. F rst row s mandatory. Rows fo ow ng one ment on ng zero can be de eted.
A ka ne Phosphatase	>1.5 ULN	Enzymes act v t es must be expressed n ULN, not n IU/L. Concept paper on DILI - FDA draft Gu dance Oct 2007. Interna DILI WG Oct 2008.
Tota B rub n	>1.5 ULN >2 ULN	Must be expressed n ULN, not n µmo /L or mg/L. Categor es are cumu at ve. Concept paper on DILI - FDA draft Gu dance Oct 2007. Interna DILI WG Oct 2008.
Conjugated B rub n	>35% Tota B rub n and TBILI>1.5 ULN	Conjugated b rub n dosed on a case-by-case bas s.
ALT and Tota B rub n	ALT>3 ULN and TBILI>2 ULN	Concept paper on DILI - FDA draft Gu dance Oct 2007. Interna DILI WG Oct 2008. To be counted w th n a same treatment phase, whatever the nterva between measurement.

CRITERIA for POTENTIALLY CLINICALLY SIGNIFICANT ABNORMALITIES
for Phase 2/3 studies (oncology excepted)
(From BTD-009536 May 21, 2014)

Parameter	PCSA	Comments
CPK	>3 ULN >10 ULN	FDA Feb 2005. Am J Card o Apr 2006. Categories are cumulative. First row is mandatory. Rows following one mentioned on zero can be deleted.
CLcr (mL/min)	<15 (end stage renal disease)	FDA draft Guidance 2010.
(Estimated creatinine clearance based on the Cockcroft-Gault equation)	≥15 - <30 (severe decrease in GFR) ≥30 - <60 (moderate decrease in GFR) ≥60 - <90 (mild decrease in GFR) ≥90 (normal GFR)	Pharmacokinetics in patients with impaired renal function-study design, data analysis, and impact on dosing and labeling.
eGFR (mL/min/1.73 m ²)	<15 (end stage renal disease)	FDA draft Guidance 2010.
(Estimate of GFR based on an MDRD equation)	≥15 - <30 (severe decrease in GFR) ≥30 - <60 (moderate decrease in GFR) ≥60 - <90 (mild decrease in GFR) ≥90 (normal GFR)	Pharmacokinetics in patients with impaired renal function-study design, data analysis, and impact on dosing and labeling.
Creatinine	≥150 μmo/L (Adults) ≥30% change from baseline ≥100% change from baseline	Benichou C, 1994.
Uric Acid		Harrison- Principles of Internal Medicine 17 th Ed, 2008.
Hyperuricemia	>408 μmo/L	
Hypouricemia	<120 μmo/L	
Blood Urea Nitrogen	≥17 mmol/L	
Cholesterol	<80 mmol/L >115 mmol/L	
Sodium	≤129 mmol/L ≥160 mmol/L	
Potassium	<3 mmol/L ≥5.5 mmol/L	FDA Feb 2005.
Total Cholesterol	≥7.74 mmol/L	Threshold for therapeutic intervention.
Triglycerides	≥4.6 mmol/L	Threshold for therapeutic intervention.
Lipase	≥3 ULN	
Amylase	≥3 ULN	

CRITERIA for POTENTIALLY CLINICALLY SIGNIFICANT ABNORMALITIES
for Phase 2/3 studies (oncology excepted)
(From BTD-009536 May 21, 2014)

Parameter	PCSA	Comments
Glucose		
Hypoglycemia	≤3.9 mmol/L and <LLN	ADA May 2005.
Hyperglycemia	≥11.1 mmol/L (unfasted); ≥7 mmol/L (fasted)	ADA Jan 2008.
HbA1c	>8%	
Albumin	≤25 g/L	
CRP	>2 ULN or >10 mg/L (if ULN not provided)	FDA Sept 2005.
Hematology		
WBC	<3.0 Giga/L (Non-Back); <2.0 Giga/L (Back) ≥16.0 Giga/L	Increase in WBC: not relevant. To be interpreted only if no differential count available.
Lymphocytes	>4.0 Giga/L	
Neutrophils	<1.5 Giga/L (Non-Back); <1.0 Giga/L (Back)	International Consensus meeting on drug-induced blood cytopenias, 1991. FDA criteria.
Monocytes	>0.7 Giga/L	
Basophils	>0.1 Giga/L	
Eosinophils	>0.5 Giga/L or >ULN (if ULN ≥0.5 Giga/L)	Harrison- Principles of Internal Medicine 17 th Ed, 2008.
Hemoglobin	≤115 g/L (Male); ≤95 g/L (Female) ≥185 g/L (Male); ≥165 g/L (Female) Decrease from Baseline ≥20 g/L	Criteria based upon decrease from baseline are more relevant than based on absolute value. Other categories for decrease from baseline can be used (≥30 g/L, ≥40 g/L, ≥50 g/L).
Hematocrit	≤0.37 v/v (Male) ; ≤0.32 v/v (Female) ≥0.55 v/v (Male) ; ≥0.5 v/v (Female)	
RBC	≥6 Tera/L	Unspecific category required for particular drug development, the analysis is redundant with that of Hb. Otherwise, consider FDA criteria.
Platelets	<100 Giga/L ≥700 Giga/L	International Consensus meeting on drug-induced blood cytopenias, 1991.

**CRITERIA for POTENTIALLY CLINICALLY SIGNIFICANT ABNORMALITIES
for Phase 2/3 studies (oncology excepted)
(From BTD-009536 May 21, 2014)**

Parameter	PCSA	Comments
Urinalysis		
pH	≤4.6 ≥8	
Vital signs		
HR	≤50 bpm and decrease from base line ≥20 bpm ≥120 bpm and increase from base line ≥20 bpm	To be applied for a positions (including missing) except STANDING.
SBP	≤95 mmHg and decrease from base line ≥20mmHg ≥160 mmHg and increase from base line ≥20 mmHg	To be applied for a positions (including missing) except STANDING.
DBP	≤45 mmHg and decrease from base line ≥10 mmHg ≥110 mmHg and increase from base line ≥10 mmHg	To be applied for a positions (including missing) except STANDING.
Orthostatic Hypotension		
Orthostatic SDB	≤-20 mmHg	
Orthostatic DBP	≤-10 mmHg	
Weight	≥5% increase from base line ≥5% decrease from base line	FDA Feb 2007.

**CRITERIA for POTENTIALLY CLINICALLY SIGNIFICANT ABNORMALITIES
for Phase 2/3 studies (oncology excepted)
(From BTD-009536 May 21, 2014)**

Parameter	PCSA	Comments
ECG		Ref: ICH E14 guidance (2005) and E14 Q&A (2012), and Cardiac Safety Research Consortium White Paper on PR and QRS (Nada et al. Am Heart J. 2013;165(4):489-500).
HR	<50 bpm	Categories are cumulative.
	<50 bpm and decrease from baseline ≥ 20 bpm	
	<40 bpm	
	<40 bpm and decrease from baseline ≥ 20 bpm	
	<30 bpm	
	<30 bpm and decrease from baseline ≥ 20 bpm	Categories are cumulative.
	>90 bpm	
	>90 bpm and increase from baseline ≥ 20 bpm	
	>100 bpm	
	>100 bpm and increase from baseline ≥ 20 bpm	
PR	>120 bpm	Categories are cumulative.
	>120 bpm and increase from baseline ≥ 20 bpm	
	>200 ms	
	>200 ms and increase from baseline $\geq 25\%$	
	>220 ms	
QRS	>220 ms and increase from baseline $\geq 25\%$	Categories are cumulative.
	>240 ms	
	>240 ms and increase from baseline $\geq 25\%$	
QT	>500 ms	
QTc	Absolute values (ms)	To be applied to any kind of QT correction formula. Absolute values categories are cumulative.
	>450 ms	QTc >480 ms and Δ QTc >60 ms are the 2 PCSA categories to be identified in individual patients.
	>480 ms	
	>500 ms	
	Increase from baseline	
	Increase from baseline [30-60] ms	
Increase from baseline >60 ms		

Statistical Analysis Plan

Version:3

Lexicon Pharmaceuticals, inc. Protocol No. EFC14838

Date of Issue: 03-Apr-2020

Covance Study ID: 000000155206

